4. PATIENT SELECTION CRITERIA

The patient population should be selected without bias.

Investigator(s) should keep a record, the patient screening log, of patients who entered pre-study screening.

Each patient should meet all of the inclusion criteria and none of the exclusion criteria for this study. Under no circumstances can there be exceptions to this rule.

4.1 Inclusion criteria

For inclusion in the study patients should fulfil the following criteria:

1. Provision of signed, written and dated informed consent prior to any study specific procedures
2. Male or female aged 18 years or older
3. Patients must have EITHER
 - Histologically- or cytologically-documented NSCLC who present with Stage IIIB/ Stage IV disease (according to Version 7 of the International Association for the Study of Lung Cancer Staging Manual in Thoracic Oncology [IASLC Staging Manual in Thoracic Oncology]), OR
 - Recurrent or progressive disease following multimodal therapy (radiation therapy, surgical resection, or definitive chemoradiation therapy for locally advanced disease)
4. Patients must have received at least 2 prior systemic treatment regimens for treatment of NSCLC
5. Patients must have experienced disease progression or recurrence after both a platinum-based chemotherapy regimen and at least 1 additional systemic therapy
 - Patients with tumours with activating *EGFR* TK mutations must have received an EGFR TKI and patients with tumours that are *ALK* fusion positive must have received an ALK TKI, given before or after the platinum-based chemotherapy regimen
 - Maintenance therapy following platinum doublet-based chemotherapy is not considered a separate regimen of therapy
 - Prior platinum-containing adjuvant, neoadjuvant or definitive chemoradiation therapy given for locally advanced disease is considered first-line therapy only if

recurrent (local or metastatic) disease developed within 6 months of completing therapy. Patients with recurrent disease >6 months must also have progressed after a subsequent platinum-based chemotherapy regimen given to treat the recurrence.

6. Patient's tumour sample must be PD-L1 positive ($\geq 25\%$ of tumour cells with membrane staining [Cohorts 1 and 2]) or PD-L1 positive with $\geq 90\%$ of tumour cells with membrane staining (Cohort 3): either recent or archival sample) based on central assessment. Sample requirements as follows:

- A mandatory provision of a recent (≤ 3 months) tumour biopsy taken following the completion of the most recent systemic anti-cancer therapy, except if technically not feasible and after discussion with the study physician (for collection and processing procedures, refer to Section 6.6.1 and the Laboratory Manual). Tumour lesions planned for biopsy must not be used as index lesions for assessment of disease
AND
- Provision of an archived tumour tissue block (or at least 10 newly cut unstained slides) where such samples exist in a quantity sufficient to allow for analysis (refer to Section 6.6.1 and the Laboratory Manual for details).

Additional biopsies may be performed to test for PD-L1 status at the Investigator's discretion.

7. Patients must have measurable disease, at least 1 lesion, not previously irradiated, which can be accurately measured at baseline as ≥ 10 mm in the longest diameter (except lymph nodes that must have short axis ≥ 15 mm) with CT or MRI and which is suitable for accurate repeated measurements per RECIST v1.1 guidelines

8. Life expectancy ≥ 12 weeks at Day 1

9. World Health Organisation (WHO) Performance Status of 0 or 1

10. Evidence of post-menopausal status, or negative urinary or serum pregnancy test for female pre-menopausal patients. Women will be considered post-menopausal if they are amenorrhic for 12 months without an alternative medical cause. The following age-specific requirements apply:

- Women < 50 years old would be considered post-menopausal if they have been amenorrhic for 12 months or more following cessation of exogenous hormonal treatments and with luteinizing hormone and follicle-stimulating hormone levels in the post-menopausal range for the institution
- Women ≥ 50 years of age would be considered post-menopausal if they have been amenorrhic for 12 months or more following cessation of all exogenous hormonal treatments, radiation-induced oophorectomy with last menses > 1 year ago,

chemotherapy-induced menopause with >1 year interval since last menses, or surgical sterilisation (bilateral oophorectomy or hysterectomy).

11. Adequate organ and marrow function as defined below:

- Absolute neutrophil count $>1.5 \times 10^9/L$ (1500 per mm^3)
- Platelets $>100 \times 10^9/L$ (100,000 per mm^3)
- Haemoglobin ≥ 9.0 g/dL (5.59 mmol/L).
- Serum creatinine CL >40 mL/min by the Cockcroft-Gault formula (Cockcroft and Gault 1976) or by 24-hour urine collection for determination of creatinine clearance:

Males:

$$\text{Creatinine CL (mL/min)} = \frac{\text{Weight (kg)} \times (140 - \text{Age})}{72 \times \text{serum creatinine (mg/dL)}}$$

Females:

$$\text{Creatinine CL (mL/min)} = \frac{\text{Weight (kg)} \times (140 - \text{Age})}{72 \times \text{serum creatinine (mg/dL)}} \times 0.85$$

- Serum bilirubin ≤ 1.5 x upper limit of normal (ULN). This will not apply to patients with confirmed Gilbert's syndrome (persistent or recurrent hyperbilirubinaemia that is predominantly unconjugated in the absence of evidence of haemolysis or hepatic pathology) who will be allowed in consultation with their physician.
- In patients with no liver metastasis: AST and ALT ≤ 2.5 x ULN
- In patients with liver metastasis: AST or ALT ≤ 5 x ULN.

Genetics research study (optional)

For inclusion in the optional (DNA) genetics research study patients must fulfil the following criteria:

- Provide informed consent for the genetic sampling and analyses.

If a patient declines to participate in the genetics research, there will be no penalty or loss of benefit to the patient. A patient who declines genetics research participation will not be excluded from any other aspect of the main study.

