4.2 Exclusion criteria

Patients should not enter the study if any of the following exclusion criteria are fulfilled:

1. Involvement in the planning and/or conduct of the study (applies to both AstraZeneca/MedImmune staff and/or staff at the study site)
2. Either:
 - Previous drug assignment in the present study, OR
 - Prior treatment in a previous durvalumab (MEDI4736) clinical study
3. Participation in another clinical study with an investigational product during the last 4 weeks
4. Concurrent enrolment in another clinical study, unless it is an observational (non-interventional) clinical study or the follow-up period of an interventional study
5. Mixed small cell and NSCLC histology
6. Receipt of any investigational drug within 4 weeks prior to the first dose of MEDI4736
7. Receipt of the last dose of anti-cancer therapy (chemotherapy, immunotherapy, endocrine therapy, targeted therapy, biologic therapy, tumour embolisation, monoclonal antibodies) ≤ 21 days prior to the first dose of MEDI4736 (≤ 14 days prior to the first dose of MEDI4736 for patients who have received prior TKIs [eg, erlotinib, gefitinib and crizotinib] and within 6 weeks for nitrosourea or mitomycin C). If sufficient wash-out time has not occurred due to the schedule or PK properties of an agent, a longer wash-out period will be required, as agreed by AstraZeneca/MedImmune and the investigator.
8. Current or prior use of immunosuppressive medication within 28 days before the first dose of MEDI4736, with the exceptions of intranasal and inhaled corticosteroids or systemic corticosteroids at physiological doses, which are not to exceed 10 mg/day of prednisone, or an equivalent corticosteroid
9. Prior exposure to any anti-PD-1 or anti-PD-L1 antibody
10. Any unresolved toxicity CTCAE $>$ Grade 2 from previous anti-cancer therapy. Patients with irreversible toxicity that is not reasonably expected to be exacerbated by the investigational product may be included (eg, hearing loss) after consultation with the AstraZeneca/MedImmune study physician.
11. Any prior Grade ≥ 3 immune-related adverse event (irAE) while receiving any previous immunotherapy agent, or any unresolved irAE $>$ Grade 1

12. Any concurrent chemotherapy, immunotherapy, biologic or hormonal therapy for cancer treatment. NOTE: Local treatment of isolated lesions, excluding target lesions, for palliative intent is acceptable (eg, by local surgery or radiotherapy).

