4.3 Criteria for Treatment through Progression of Disease and Retreatment

Patients with rapid tumour progression or with symptomatic progression that requires urgent medical intervention (eg, central nervous system metastasis, respiratory failure due to tumour compression, spinal cord compression) will not be eligible for continuing MEDI4736.

For all patients who completed the first 12 month period of treatment with MEDI4736 and had CR, PR, or SD at completion, retreatment during follow up would be offered on the basis of a patient having objective RECIST 1.1 disease progression with or without confirmation.

For all patients who are treated through progression, or patients who achieve disease control [ie, CR, PR, or SD] at 12 months and restart treatment upon evidence of PD during follow-up, the investigator should ensure patients do not have any significant, unacceptable or irreversible toxicities that indicate continuing or restarting treatment would not further benefit the patient. Patients who progressed during the first 12 months are not allowed re-treatment. In addition, the investigator should ensure patients meet the following inclusion criteria (criteria number from section 4.1):

- The patient must provide signed, written and dated retreatment or treatment through progression informed consent (criterion 1). These consent documents will specify that treatment beyond initial evidence of PD or re-treatment upon progression during follow up is not the standard of care and that alternative treatment options, either locally licensed treatments or other clinical trials, are available for this patient population.
- Meet serum creatinine CL >40 mL/min by the Cockcroft-Gault formula (or by 24-hour urine collection as defined by the formula in protocol inclusion criterion 11) and the criterion for AST/ALT.

The patient should not enter retreatment if any of the following exclusion criteria are fulfilled:

- Concurrent enrolment in another clinical study, unless it is an observational (non-interventional) clinical study or the follow-up period of an interventional study (criterion 4)
- Current or prior use of immunosuppressive medication within 28 days before the first dose of MEDI4736, with the exceptions of intranasal and inhaled corticosteroids or systemic corticosteroids at physiological doses, which are not to exceed 10 mg/day of prednisone, or an equivalent corticosteroid (criterion 8)

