	Grade 2 (AST or ALT > 3 to 5 times ULN and/or TB >1.5-3.0 times ULN)	Hold Study drug/study regimen dose until grade 2 resolution to ≤ Grade 1 
 • If toxicity worsens then treat as Grade 3 or Grade 4 • If improves to baseline then treat at next scheduled treatment date Study drug/study regimen can be resumed at the next scheduled dose once event stabilizes to grade ≤1 and 5-7 days have passed after completion of steroid taper	For Grade 2 AST or ALT and or TB elevation : 
 - Regular and frequent checking of LFTs (e.g. every 1-2 days) until elevations of these are improving or resolved. - If no resolution to ≤ Grade 1 in 1-2 days, discuss with study physician. - If event is persistent (> 3-5 days) or worsens, promptly start prednisone 1-2mg/kg/day or IV equivalent. - If still no improvement within 3-5 days despite 1-2mg/kg/day of prednisone or IV equivalent, consider additional workup and prompt treatment with IV methylprednisolone 2-4mg/kg/day started. - If still no improvement within 3-5 days despite 2-4mg/kg/day of IV methylprednisolone, promptly start immunosuppressives (mycophenolate mofetil)³ . Discuss with study physician if mycophenolate mofetil is not available. Infliximab should NOT be used. - Once improving, gradually taper steroids over ≥28 days and consider prophylactic antibiotics, antifungals and anti PCP treatment (please refer to

³ ASCO Educational Book 2015 “Managing Immune Checkpoint Blocking Antibody Side Effects” , by Michael Postow MD

Dosing Modification and Toxicity Management Guidelines for Immune-mediated, Infusion Related, and Non Immune-mediated Reactions (MEDI4736 Monotherapy or Combination therapy with Tremelimumab or Tremelimumab monotherapy)

	Grade of the Event (NCI CTCAE version 4.03)	Dose Modifications	Toxicity Management
			current NCCN guidelines for treatment of cancer-related infections [Category 2B recommendation])

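### With liver metastases, inclusion criterion 11 caps only one of AST and ALT as worded, and Section 4.3 reuses that limit

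*Protocol*

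**What the plan says.** Criterion 11 in Protocol Section 4.1 defines adequate organ and marrow function. Its two transaminase bullets stand next to each other:

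- "In patients with no liver metastasis: AST and ALT ≤ 2.5 x ULN"
- "In patients with liver metastasis: AST or ALT" ≤ 5 x ULN

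Section 4 says of the entry criteria: "Under no circumstances can there be exceptions to this rule".

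Section 4.3 lists what must be met again before a patient is treated through progression or retreated. From criterion 11 it takes creatinine clearance, "as defined by the formula in protocol inclusion criterion 11) and the criterion for AST/ALT". It states no transaminase limit of its own and does not carry over the bilirubin limit.

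**The concern.** The two bullets have the same purpose but use different connectives. In an upper limit that must be satisfied, 'and' caps both enzymes, while 'or' is satisfied by the lower of the two. So the bullet for patients with liver metastases, whose transaminases are most likely to be raised at entry, leaves the higher enzyme without a bound.

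The contrast with the line above means a site could take the difference as intended. Sites can therefore apply the rule in two ways, and the protocol plans 100 to 150 sites. Section 5.5.3.1 lists transaminase increases and hepatitis among the adverse events of special interest observed with the drug. A patient who enters with one enzyme already far above 5 x ULN is exposed to a risk the criterion was presumably meant to exclude, and later liver toxicity in that patient is harder to attribute.

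**Working it through.** No sample size, power or interval depends on this point. The check is a reading of the criteria side by side.

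**The rule as written and as repaired** (values in multiples of ULN, patient with liver metastases)

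- As written: AST ≤ 5 or ALT ≤ 5. This is the same as min(AST, ALT) ≤ 5, so max(AST, ALT) is unbounded.
- With 'and': AST ≤ 5 and ALT ≤ 5. This is the same as max(AST, ALT) ≤ 5.

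| ALT | AST | As written | With 'and' |
|---|---|---|---|
| 4 | 4 | passes | passes |
| 4 | 12 | passes | fails |
| 12 | 12 | fails | fails |

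The values are illustrative. The two readings differ only when one enzyme is at or below 5 x ULN and the other is above it. Without liver metastases, "In patients with no liver metastasis: AST and ALT" already gives max(AST, ALT) ≤ 2.5.

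**Does another criterion supply the missing ceiling?**

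- *Exclusion 10* ("Any unresolved toxicity CTCAE" above Grade 2). Appendix G defines Grade 2 hepatitis as "AST or ALT > 3 to 5 times ULN", and Grade 3 starts above 5 x ULN on either enzyme. An elevation left by earlier anti-cancer therapy is therefore generally limited to 5 x ULN. The limit is not absolute, because irreversible toxicity can be accepted after consultation with the study physician. An elevation caused by metastases is not treatment toxicity, so this exclusion does not reach it.
- *Exclusion 28* leaves room for the investigator's opinion but gives no number.
- *Bilirubin* must be at or below 1.5 x ULN at entry (confirmed Gilbert's syndrome exempt). That limits a different analyte and does not bound a transaminase.

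**The same word in Appendix G.** There, 'or' describes a trigger: the grade is reached when either enzyme is high, which is the cautious reading. In an entry condition that a low value satisfies, the same word has the opposite effect. The two texts do not contradict each other, since Section 5.5.3 confines the Appendix G guidance to events judged related to study drug.

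**Section 4.3.** The AST/ALT criterion is imported by reference, so the connective comes with it. With bilirubin not listed, AST/ALT is the only liver laboratory value the section names. Its list of exclusions is introduced for entry to retreatment. On that wording exclusions 10 and 28 are not tied to treatment through progression, although Sections 3.1 and 6.3.1 suggest that both situations were meant.

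**The case against.** The strongest reply is that the intent is obvious and the exposed group very narrow. To benefit from the literal wording a patient needs liver metastases, one enzyme at or below 5 x ULN with the other above it, bilirubin within 1.5 x ULN, performance status 0 or 1, a life expectancy of at least 12 weeks, no known hepatitis B or C, no treatment cause for the elevation, and an investigator who sees no reason to use exclusion 28. Liver function results must also be available before each infusion. Section 4.3 has its own safeguards: it bars patients with significant or irreversible toxicity, stops continued treatment when progression is rapid or needs urgent intervention, and repeats exclusions 10, 23 and 28 for retreatment. The no-exceptions sentence forbids waiving a criterion; it does not oblige a site to enrol everyone who literally passes one bullet.

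All of this is correct, and it reduces the number of patients concerned. It does not remove the defect, because none of these safeguards puts a number on the second enzyme when the cause is metastatic. A no-exceptions safety threshold should not depend on sites guessing what was meant.

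It can also be said that changing an eligibility limit in a running study costs more than one word. That point stands and is counted in the cost of the fix.

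**Conclusion.** The concern holds. Read literally, criterion 11 caps only the lower of AST and ALT in patients with liver metastases, and Section 4.3 carries the same limit into treatment through progression and retreatment. The remaining gap is metastasis-related elevation, together with any irreversible treatment-related elevation accepted under the exception in exclusion 10.

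The conclusion rests on the literal wording. The sponsor very probably meant to cap both enzymes, and many sites may apply it that way. The protocol does not give the number of patients affected; it is probably small. The planned sample size, the ORR analysis and its confidence intervals do not change. The point should be corrected because it is an operative safety rule, not because it alters any result.

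**What to change.** In the liver-metastasis bullet of criterion 11, replace 'or' with 'and', so that both AST and ALT must be at or below 5 x ULN. This matches the structure of the bullet above it and the 5 x ULN level that exclusion 10 already implies for treatment-caused elevations. Section 4.3 refers back to the criterion and needs no separate edit.

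The change in text is one word, with possibly a few extra screen failures. Since recruitment has begun, the change belongs in a protocol amendment with the approvals described in Section 8.5, and patients enrolled before and after it will have entered under different wordings. It can go into the next amendment.

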4.2 Exclusion criteria

Patients should not enter the study if any of the following exclusion criteria are fulfilled:

1. Involvement in the planning and/or conduct of the study (applies to both AstraZeneca/MedImmune staff and/or staff at the study site)
2. Either:
 - Previous drug assignment in the present study, OR
 - Prior treatment in a previous durvalumab (MEDI4736) clinical study
3. Participation in another clinical study with an investigational product during the last 4 weeks
4. Concurrent enrolment in another clinical study, unless it is an observational (non-interventional) clinical study or the follow-up period of an interventional study
5. Mixed small cell and NSCLC histology
6. Receipt of any investigational drug within 4 weeks prior to the first dose of MEDI4736
7. Receipt of the last dose of anti-cancer therapy (chemotherapy, immunotherapy, endocrine therapy, targeted therapy, biologic therapy, tumour embolisation, monoclonal antibodies) ≤ 21 days prior to the first dose of MEDI4736 (≤ 14 days prior to the first dose of MEDI4736 for patients who have received prior TKIs [eg, erlotinib, gefitinib and crizotinib] and within 6 weeks for nitrosourea or mitomycin C). If sufficient wash-out time has not occurred due to the schedule or PK properties of an agent, a longer wash-out period will be required, as agreed by AstraZeneca/MedImmune and the investigator.
8. Current or prior use of immunosuppressive medication within 28 days before the first dose of MEDI4736, with the exceptions of intranasal and inhaled corticosteroids or systemic corticosteroids at physiological doses, which are not to exceed 10 mg/day of prednisone, or an equivalent corticosteroid
9. Prior exposure to any anti-PD-1 or anti-PD-L1 antibody
10. Any unresolved toxicity CTCAE $>$ Grade 2 from previous anti-cancer therapy. Patients with irreversible toxicity that is not reasonably expected to be exacerbated by the investigational product may be included (eg, hearing loss) after consultation with the AstraZeneca/MedImmune study physician.
11. Any prior Grade ≥ 3 immune-related adverse event (irAE) while receiving any previous immunotherapy agent, or any unresolved irAE $>$ Grade 1

12. Any concurrent chemotherapy, immunotherapy, biologic or hormonal therapy for cancer treatment. NOTE: Local treatment of isolated lesions, excluding target lesions, for palliative intent is acceptable (eg, by local surgery or radiotherapy).
13. Receipt of radiation therapy within 4 weeks prior to starting MEDI4736. Limited field of radiation for palliation within 2 weeks of the first dose of study treatment is allowed, provided:
 - The lung is not in the radiation field
 - Irradiated lesion(s) cannot be used as target lesions.
14. Recent major surgery within 4 weeks prior to entry into the study (excluding the placement of vascular access) that would prevent administration of investigational product
15. Active or prior documented autoimmune disease within the past 2 years. NOTE: Patients with vitiligo, Grave's disease, or psoriasis not requiring systemic treatment (within the past 2 years) are not excluded.
16. Active or prior documented inflammatory bowel disease (eg, Crohn's disease, ulcerative colitis)
17. History of primary immunodeficiency
18. History of allogeneic organ transplant
19. History of hypersensitivity to MEDI4736 or any excipient
20. Brain metastases or spinal cord compression unless asymptomatic, treated and stable off steroids and anti-convulsants for at least 1 month prior to entry into the study
21. History of leptomeningeal carcinomatosis
22. Mean QT interval corrected for heart rate (QTc) ≥ 470 ms calculated from 3 electrocardiograms (ECGs) using Bazett's Correction
23. Uncontrolled intercurrent illness including, but not limited to, ongoing or active infection, symptomatic congestive heart failure, uncontrolled hypertension, unstable angina pectoris, cardiac arrhythmia, active peptic ulcer disease or gastritis, active bleeding diatheses including any patient known to have evidence of acute or chronic hepatitis B, hepatitis C or human immunodeficiency virus (HIV), or psychiatric illness/social situations that would limit compliance with study requirements or compromise the ability of the patient to give written informed consent
24. Active infection of tuberculosis, as determined by clinical signs and symptoms

25. Receipt of live attenuated vaccination within 30 days prior to study entry or within 30 days of receiving MEDI4736
26. History of another primary malignancy except for:
 - Malignancy treated with curative intent and with no known active disease ≥ 5 years before the first dose of study drug and of low potential risk for recurrence
 - Adequately treated non-melanoma skin cancer or lentigo maligna without evidence of disease
 - Adequately treated carcinoma in situ without evidence of disease eg, cervical cancer in situ.
27. Female patients who are pregnant, breast-feeding or male or female patients of reproductive potential who are not employing an effective method of birth control.
28. Any condition that, in the opinion of the investigator, would interfere with evaluation of the investigational product or interpretation of patient safety or study results.
29. Absence of a tumour sample (archival and recent).

Genetics research study (optional)

Exclusion criteria for participation in the optional (DNA) genetics research component of the study:

- Previous allogeneic bone marrow transplant
- Non-leukocyte depleted whole blood transfusion in 120 days of genetic sample collection

Procedures for withdrawal of incorrectly enrolled patients are provided in Section 5.3.

